After baseline, changes in non-target lesions will contribute only in the assessment of complete response (i.e., a complete response is attained only with the complete disappearance of all tumor lesions, including non-target lesions) and will not be used to assess progressive disease.

CALCULATION OF SUM OF THE DIAMETERS

A sum of the diameters (longest for non-nodal lesions, short axis for nodal lesions) for all target lesions will be calculated as a measure of tumor burden.

The sum of the diameters is calculated at baseline and at each tumor assessment for the purpose of classification of tumor responses.

Sum of the Diameters at Baseline: The sum of the diameters for all target lesions identified at baseline prior to treatment on Day 1.

Sum of the Diameters at Tumor Assessment: For every on-study tumor assessment collected per protocol or as clinically indicated, the sum of the diameters at tumor assessment will be calculated using tumor imaging scans. All target lesions and all new measurable lesions that have emerged after baseline will contribute to the sum of the diameters at tumor assessment. Hence, each net percentage change in tumor burden

Appendix 3

Modified Response Evaluation Criteria in Solid Tumors (cont.)

per assessment with use of modified RECIST accounts for the size and growth kinetics of both old and new lesions as they appear.

RESPONSE CRITERIA

Evaluation of Target Lesions

Complete Response (CR): Disappearance of all target lesions. Lymph nodes that shrink to < 10 mm short axis are considered normal.

Partial Response (PR): At least a 30% decrease in the sum of the diameters of all target and all new measurable lesions, taking as reference the baseline sum of diameters, in the absence of CR.

Note: The appearance of new measurable lesions is factored into the overall tumor burden but *does not automatically qualify as progressive disease* until the sum of the diameters increases by $\geq 20\%$ when compared with the sum of the diameters at nadir.

Stable Disease (SD): Neither sufficient shrinkage to qualify for PR nor sufficient increase to qualify for PD, taking as reference the smallest sum of the diameters while on study.

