Progressive Disease (PD): At least a 20% increase in the sum of diameters of all target and all new measurable lesions, taking as reference the smallest sum on study (this includes the baseline sum if that is the smallest on study). In addition to the relative increase of 20%, the sum must also demonstrate an absolute increase of at least 5 mm.

Impact of New Lesions on Modified RECIST

New lesions alone do not qualify as progressive disease. However, their contribution to total tumor burden is included in the sum of the diameters, which is used to determine the overall modified RECIST tumor response.

EVALUATION OF BEST OVERALL RESPONSE USING MODIFIED RECIST

TIMEPOINT RESPONSE

It is assumed that at each protocol-specified timepoint, a response assessment occurs. [Table 1](#) provides a summary of the overall response status calculation at each timepoint for patients who have measurable disease at baseline.

MISSING ASSESSMENTS AND INEVALUABLE DESIGNATION

When no imaging/measurement is done at all at a particular timepoint, the patient is not evaluable (NE) at that timepoint. If only a subset of lesion measurements are made at an assessment, usually the case is also considered NE at that timepoint, unless a

Appendix 3

Modified Response Evaluation Criteria in Solid Tumors (cont.)

convincing argument can be made that the contribution of the individual missing lesion(s) would not change the assigned time point response. This would be most likely to happen in the case of PD. For example, if a patient had a baseline sum of 50 mm with three measured lesions and at follow-up only two lesions were assessed but those gave a sum of 80 mm, the patient will have achieved PD status, regardless of the contribution of the missing lesion.

Table 1 Modified RECIST Timepoint Response Definitions

% Change in Sum of the Diameters (Including Measurable New Lesions When Present)	Target Lesion Definition	Non-Target Lesion Definition	New Measurable Lesions	New Unmeasurable Lesions	Overall Modified RECIST Timepoint Response
– 100% ^a	CR	CR	No	No	CR
– 100% ^a	CR	Non-CR or not all evaluated	No	No	PR
≤ – 30%	PR	Any	Yes or no	Yes or no	PR
> – 30% to < + 20%	SD	Any	Yes or no	Yes or no	SD
Not all evaluated	Not evaluated	Any	Yes or no	Yes or no	NE
≥ + 20%	PD	Any	Yes or no	Yes or no	PD

CR = complete response; NE = not evaluable; PD = progressive disease; PR = partial response; RECIST = Response Evaluation Criteria in Solid Tumors; SD = stable disease.

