^a When lymph nodes are included as target lesions, the % change in the sum of the diameters may not be 100% even if complete response criteria are met since a normal lymph node is defined as having a short axis of < 10 mm. Any pathological lymph nodes (whether target or non-target) must have reduction in short axis to < 10 mm in order to meet the definition of CR.

BEST OVERALL RESPONSE: ALL TIMEPOINTS

The best overall response is determined once all the data for the patient are known.

Appendix 3

Modified Response Evaluation Criteria in Solid Tumors (cont.)

The best overall response according to modified RECIST is interpreted as below:

- **CR:** Complete disappearance of all tumor lesions (target and non-target) and no new measurable or unmeasurable lesions, confirmed by a consecutive assessment \geq 4 weeks from the date first documented. All lymph nodes short axes must be < 10 mm.
- **PR:** Decrease in the sum of the diameters of all target and all new measurable lesions $\geq 30\%$ relative to baseline, in the absence of CR, confirmed by a consecutive assessment \geq 4 weeks from the date first documented.
- **SD:** Criteria for CR, PR, and PD are not met.
- **PD:** Increase in the sum of the diameters of all target and all new measurable lesions $\geq 20\%$ relative to the nadir, which may be confirmed by a consecutive assessment \geq 4 weeks from the date first documented as follows:

The confirmatory assessment shows an additional measurable increase in tumor burden as measured by the sum of the diameters of all target and all new measurable lesions.

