3.4.1.5 Duration of Response

DOOR according to RECIST 1.1 is defined as the time from the first tumor assessment that supports the patient's objective response (CR or PR, whichever is first reported) to documented disease progression as determined by the investigator according to RECIST v1.1 or death from any cause, whichever occurs first, among patients who have a best overall response as CR or PR.

Patients who are alive and have not experienced disease progression at the time of clinical cut-off date will be censored at the time of the last tumor assessment date. If no tumor assessments were performed after the date of the first occurrence of a CR or PR, DOOR will be censored at the date of the first occurrence of a CR or PR plus 1 day.

3.4.1.6 Objective Response Rate, Progression Free Survival, and Duration of Objective Response per Modified RECIST

ORR, PFS, and DOOR analyses using modified RECIST criteria. The investigator-assessed ORR is defined as the proportion of patients whose confirmed best overall response is either a PR or CR per modified RECIST. An estimate of ORR and its 95% CI will be calculated for the ITT population using the Clopper-Pearson method.

For patients experienced an objective response (CR or PR per modified RECIST) during the study as assessed by the investigator, DOOR is defined as the duration from the first tumor assessment that supports the patient's objective response (CR or PR, whichever is first recorded) to disease progression or death due to any cause, whichever occurs first.

Patients who are alive and who have not experienced disease progression at the time of analysis will be censored at the last tumor assessment date. DOOR will be assessed using Kaplan-Meier methodology.

PFS by modified RECIST is defined as the time from first treatment taken to disease progression as determined by the investigator per modified RECIST or death from any cause, whichever occurs first. A patient is considered to have disease progression by modified RECIST if either of the following conditions were met:

- a) Modified RECIST criteria for progression were met at a tumor assessment and no subsequent tumor assessment was performed.
- b) Modified RECIST criteria for progression were met at a tumor assessment, and at the subsequent tumor assessment, the criteria for confirmed progression by modified RECIST were also met.

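### Appendix 3 defines modified RECIST progression with a 5 mm minimum increase, but Table 1 and the best-response rule omit it, and Table 1 names no reference sum

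*Protocol*

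**What the plan says.** Protocol Appendix 3 states the modified RECIST rule for progression in several places.

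- **Response Criteria, Progressive Disease.** The sum of target and new measurable lesions must rise by at least 20%, "taking as reference the smallest sum on study (this includes the baseline sum if that is the smallest on study". A second condition follows: "In addition to the relative increase of 20%, the sum must also demonstrate an absolute increase of at least 5 mm".
- **Table 1, timepoint response.** One percentage column, headed "Change in Sum of the Diameters (Including Measurable New Lesions When Present", sorts every assessment. The PD row is +20% or more and the stable-disease row stops below +20%. There is no millimetre condition, and the column does not say whether change is from baseline or from nadir.
- **Best Overall Response, PD.** "Increase in the sum of the diameters of all target and all new measurable lesions" of 20% or more, "relative to the nadir, which may be confirmed by a consecutive assessment". The 5 mm condition is absent.
- **Partial response.** The reference is the baseline sum, in both the Response Criteria and the best-response list.

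Appendix 2 (RECIST v1.1) keeps the 5 mm condition for target lesions.

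SAP 3.4.1.6 repeats neither threshold. It counts progression under condition a) if "Modified RECIST criteria for progression were met at a tumor assessment and no subsequent tumor assessment was performed", or under condition b) if progression is confirmed at the subsequent assessment. In case b) the date is that of the first scan meeting the criteria.

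**The concern.** A definition and the rules that apply it should give the same answer. Here they do not when the smallest sum is small, and nothing in either document says which prevails. The 5 mm floor stops a change of a few millimetres in a small sum from counting as growth. Without it, modified RECIST, which is meant to tolerate apparent progression better than RECIST v1.1, can call PD on target lesions where RECIST v1.1 does not.

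Response is assessed by investigators at about 140 sites. Two investigators working from different parts of the same appendix could classify the same scan differently, and the SAP takes the investigator's call into PFS and DOR per modified RECIST.

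**Working it through.** **1. Where the wordings part.** A 20% rise is smaller than 5 mm when 0.20 × nadir < 5, that is, when nadir < 25 mm. The smallest rise that counts as PD is:

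| Smallest sum (mm) | 20% only (mm) | 20% and 5 mm (mm) |
|---|---|---|
| 10 | 2.0 | 5 |
| 15 | 3.0 | 5 |
| 20 | 4.0 | 5 |
| 24 | 4.8 | 5 |
| 25 | 5.0 | 5 |

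A small sum can come from a small baseline as well as from a deep response: one 10 mm lesion is measurable disease under both appendices.

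**2. Examples.**
- 20 → 24 mm is +20% and +4 mm. It is stable disease by the definition, but PD by the best-response rule and by Table 1 read against nadir.
- 10 → 12 → 13 mm. The second reading is +20% (+2 mm). The third is a further increase, which is all the appendix asks of confirmation. Under the 20%-only rule this is confirmed PD at +3 mm in total, dated to the second reading. Under the definition PD is never reached.
- The appendix's own example, 50 → 80 mm, is +60% and +30 mm. It is PD under either wording and does not show which governs.

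**3. The reference sum in Table 1.** Take 100 → 40 → 60 mm. From baseline, 60/100 − 1 = −40%, which fits the PR row. From nadir, 60/40 − 1 = +50%, which fits the PD row. Table 1 gives no precedence. The text settles it: the PD threshold is 1.2 × 40 = 48 mm and the rise is 20 mm, so this is PD.

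**4. How often noise alone would cross the threshold.** The documents give no measurement error. Assume a constant true sum S and independent normal reading error with standard deviation σ at the nadir scan, the next scan and the one after.

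- 20% only: P = 1 − Φ(0.2S / (σ√(1 + 1.2²))). For S = 10, σ = 1: 1 − Φ(2/1.562) = 10.0%.
- 5 mm floor, for S below 25: P ≈ 1 − Φ(5 / (σ√2)). For σ = 2: 1 − Φ(1.768) = 3.9%.
- Confirmed: the third reading must also exceed the second (simulation of 2,000,000 patients, which also reproduces the two rates above).

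| S (mm) | σ (mm) | 20% only, one scan | 20% only, confirmed | With 5 mm, one scan | With 5 mm, confirmed |
|---|---|---|---|---|---|
| 10 | 1 | 10.0% | 1.9% | 0.02% | 0.0% |
| 10 | 2 | 26.1% | 7.1% | 3.9% | 0.4% |
| 15 | 1 | 2.7% | 0.3% | 0.02% | 0.0% |
| 15 | 2 | 16.8% | 3.9% | 3.8% | 0.4% |
| 20 | 1 | 0.5% | 0.04% | 0.02% | 0.0% |
| 20 | 2 | 10.0% | 1.9% | 3.9% | 0.4% |

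At σ = 0.5 mm and S = 10 mm the single-scan rate on 20% alone is 0.5%.

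**The case against.** The strongest reply is that the definition still governs. Its 5 mm condition is mandatory, and Table 1 only "provides a summary of the overall response status calculation at each timepoint for patients who have measurable disease at baseline". The table's PD row also carries PD in its target-lesion column, which points back to the definition. Appendix 3's comparison of the two criteria describes RECIST v1.1 progression as a 20% rise with no mention of 5 mm, although Appendix 2 requires it, so the omission looks like shorthand. Stable disease is already defined in the text as neither PR nor PD. The note on new lesions, which speaks of a 20% rise "when compared with the sum of the diameters at nadir", says only what must happen before new lesions can count as PD; it is not a separate rule.

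Most of this stands, and it rules out a reading someone might take away: that patients in this trial will progress on measurement noise. That happens only if Table 1 or the best-response rule is applied literally in place of the definition. What remains is that the best-response rule is not presented as a summary, Table 1 is titled as definitions and restates its own cut-offs, and no order of precedence is given.

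Confirmation is the second reply. A rise under 5 mm with no new lesion and no non-target progression is not RECIST v1.1 PD, so scheduled scans continue and SAP condition b) would usually apply. That removes most of the noise-driven calls, but it does not restore the floor, as 10 → 12 → 13 mm shows. Condition a) still accepts an unconfirmed call at the last scan, where the single-scan rate applies.

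A reader might also infer from the unlabelled column that PD could be measured from baseline, moving the threshold in the 100 → 40 mm example to 120 mm. The definition, the best-response rule and the new-lesion note all name nadir or the smallest sum, so the documents do not support that reading. It would also delay PD, not bring it forward.

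**Conclusion.** The inconsistency is real and the text is wrong as written, but the severity is minor. Two rules in Appendix 3 give a result that the definition excludes, for smallest sums below 25 mm only.

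The size depends on an assumed reading error and on an unknown number of patients with small sums, which the documents do not allow anyone to estimate. The 10% to 26% single-scan rates belong to a 10 mm sum, well inside the affected range; at 20 mm they are 0.5% to 10.0%.

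The reach is limited to PFS and DOR per modified RECIST, which the SAP treats as descriptive in a single-arm safety study. ORR counts confirmed CR or PR, so calling a patient PD instead of stable disease does not change it. OS and the primary safety endpoints are untouched. Nor is there a planned formal comparison of the two criteria to be distorted: the SAP reports them separately.

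**What to change.** - **Appendix 3, Table 1.** Label the CR and PR rows as change from baseline. Define the PD row as at least +20% from the smallest sum on study together with an absolute increase of at least 5 mm, and state that it takes precedence over PR and stable disease. Define stable disease as neither.
- **Appendix 3, best-response PD line.** Add the 5 mm condition.
- **SAP 3.4.1.6.** Name the Appendix 3 Progressive Disease definition as the criteria for progression.

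Because the SAP uses the investigator's determination, the appendix that sites work from has to change; citing the definition in the SAP is not enough by itself. The cost is wording, with no new data. The downside is that a few patients with small sums would progress slightly later by modified RECIST than under the 20%-only rules.

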- l. Urinalysis includes specific gravity, pH, glucose, protein, ketones, and blood.
- m. A serum pregnancy test (for women of childbearing potential, including women who have had a tubal ligation) must be performed and documented as negative within 14 days prior to Day 1. On study pregnancy tests performed every 3 treatment cycles can be conducted with serum or urine.
- n. The same radiographic procedure should be used throughout the study for each patient. A CT (with contrast) or MRI of the head must be included in screening tumor assessments for patients with known or suspected CNS disease. Results must be reviewed by the investigator before dosing at the next cycle. Patients who continue treatment beyond radiographic disease progression assessed per RECIST v1.1 should be monitored with a follow-up scan at the next scheduled tumor assessment when the scan frequency is every 6 weeks, and will be assessed

Appendix 1

Schedule of Assessments (cont.)

by modified RECIST criteria (see [Appendix 3](#)) until treatment discontinuation. If the scan frequency is every 9 weeks, a follow-up scan is recommended at 9 weeks or earlier if clinically indicated. Investigators may perform additional scans or more frequent assessments if clinically indicated.

- o. Ideally within 14 days of the start of study treatment.
- p. Patients will undergo tumor assessments at baseline, every 6 weeks \pm 5 days for the first 48 weeks following treatment initiation, and every 9 weeks thereafter until radiographic disease progression per RECIST v1.1 or (for patients who continue atezolizumab after radiographic disease progression) loss of clinical benefit as determined by the investigator (see Section [4.6.2](#) for details). Thus, tumor assessments are to continue according to schedule in patients who discontinue treatment for reasons other than disease progression or loss of clinical benefit, even if they start new anti-cancer therapy.
- q. For sites where EGFR/ALK testing is not routinely performed at local laboratories, a minimum of 7 consecutively cut slides from a most recent FFPE tumor tissue block must be submitted for EGFR/ALK testing for all patients with non-squamous NSCLC. Testing is not required for patients who have squamous NSCLC. EGFR mutation and ALK testing should be considered for patients with squamous NSCLC who are never-smokers, have mixed histology or small biopsy specimen.

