For patients who meet criterion a, the date of progression is the date of the tumor assessment that met the criteria for modified RECIST. For patients who meet criterion b, the date of progression is the date of the tumor assessment at which the modified RECIST criteria for progression were first met. Patients who did not meet either of the above criteria are not considered to have had disease progression by modified RECIST.

PFS and DOR per modified RECIST will be summarized using the Kaplan-Meier methodology.

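### A modified RECIST progression followed by a scan that was done but is not evaluable meets neither SAP progression condition, so an unrefuted progression is dropped or dated late

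*Protocol*

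**What the plan says.** SAP 3.4.1.6 defines progression for modified RECIST PFS by two conditions. Condition (a): "Modified RECIST criteria for progression were met at a tumor assessment and no subsequent tumor assessment was performed". Condition (b): PD criteria were met and, "at the subsequent tumor assessment, the criteria for confirmed progression by modified RECIST were also met". The closing rule is: "Patients who did not meet either of the above criteria are not considered to have had disease progression by modified RECIST". When (b) holds, the date is that of the first PD.

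Protocol Appendix 3 sets the status of an incomplete scan: "If only a subset of lesion measurements are made at an assessment, usually the case is also considered NE at that timepoint". Table 1 of that appendix has a matching row for lesions not all evaluated. Three neighbouring statements limit its reach:

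- A visit with no imaging is also NE: "When no imaging/measurement is done at all at a particular timepoint, the patient is not evaluable (NE) at that timepoint".
- A partial scan can still be PD. In the appendix's own example, "the patient will have achieved PD status, regardless of the contribution of the missing lesion".
- Confirmation requires more than a second PD reading: "The confirmatory assessment shows an additional measurable increase in tumor burden".

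Neither document says to skip NE visits when looking for the subsequent assessment. SAP 3.6 (missing data) covers only partial AE and medication dates and death dates. The protocol (6.6.2) defines PFS by first documented progression, but SAP section 3 states that its analyses supersede the protocol's.

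**The concern.** Condition (a) shows the intent: a PD that nothing later contradicts is an event. A PD followed by one uninformative scan is in the same position, yet the rule gives the opposite result. The scan was performed, so (a) fails. It cannot show a further increase, so (b) fails. The closing rule then makes the patient progression-free.

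This differs from a readable follow-up scan showing no further growth, which the rule is meant to let overturn a PD. PFS and DOR by modified RECIST are stated secondary endpoints, and the error runs one way: a dated event is replaced by a later event or by later censoring.

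**Working it through.** **Inputs.** Conditions (a) and (b) and the closing rule (SAP 3.4.1.6); NE status and confirmation (Protocol Appendix 3); scans every 6 weeks to week 48, then every 9 weeks (Protocol Appendix 1); censoring at the last tumor assessment (Protocol 6.6.2 for PFS; the DOR paragraph of SAP 3.4.1.6); about 600 patients.

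**Step 1: the appendix's own example.** A baseline sum of 50 mm and a partial sum of 80 mm give (80 − 50)/50 = +60% and +30 mm. Both exceed the PD thresholds of 20% and 5 mm, so that scan is PD and not NE. A partial scan of this kind can confirm an earlier PD if it also shows a further increase.

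**Step 2: scan sequences under the literal rule, and with NE scans skipped.**

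| Sequence (week) | SAP as written | NE skipped |
|---|---|---|
| SD 6, PD 12, no later imaging | PD at 12, by (a) | 12 |
| SD 6, PD 12, larger PD 18 | PD at 12, by (b) | 12 |
| SD 6, PD 12, SD 18 | no PD | no PD |
| SD 6, PD 12, NE 18, end | no PD; event at death, or censored at 18 | 12 |
| SD 6, PD 12, NE 18, larger PD 24 | PD at 24 | 12 |
| SD 48, PD 57, NE 66, larger PD 75 | PD at 75 | 57 |

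The delay is 24 − 12 = 12 weeks on 6-weekly scans and 75 − 57 = 18 weeks on 9-weekly scans. A PD that a readable scan refutes stays refuted in both columns.

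**Step 3: size, by assumption.** The documents give no NE rate. Illustrative simulation, 20,000 patients per scenario:

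- exponential time to progression, median 2, 3 or 4 months, detected at the next scheduled scan;
- 30% or 60% of patients scanned after PD;
- 2%, 5%, 10% or 20% of those scans NE, with half of the NE cases scanned again and showing larger PD;
- every evaluable follow-up scan confirms the PD;
- death after PD with median 11.1 months (the figure in Protocol 3.3.6 for patients who continued atezolizumab), and no death before PD;
- cut-off between 130 and 208 weeks.

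This makes 3 × 2 × 4 = 24 scenarios. Selected results:

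| Median (months) | Scanned after PD | NE share | Affected per 600 | 26-week PFS, SAP vs NE skipped | Median (weeks), SAP vs NE skipped |
|---|---|---|---|---|---|
| 2 | 30% | 2% | 3 | 14.9% vs 14.7% | 12 vs 12 |
| 2 | 60% | 20% | 65 | 19.8% vs 14.7% | 12 vs 12 |
| 3 | 60% | 10% | 31 | 30.4% vs 28.0% | 18 vs 18 |
| 4 | 60% | 10% | 31 | 40.4% vs 38.3% | 24 vs 18 |

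Arithmetic check: 600 × 0.30 × 0.02 = 3.6 and 600 × 0.60 × 0.20 = 72. The simulated counts of 3 and 65 are a little lower because some patients die or reach the cut-off before the follow-up scan.

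Across all 24 scenarios, 26-week PFS is too high by 0.2 to about 5 points, and the restricted mean over 104 weeks is 0.1 to 3.1 weeks too long. The median moves in 3 scenarios only, by one scan interval (18 to 24 weeks). All three have a 4-month median and an NE share of 10% or 20%.

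**The case against.** **Incomplete scans should be uncommon.** Protocol 4.5.5 requires all known disease sites to be reassessed at every tumor evaluation. A reader might infer that partial scans are built into the design because Appendix 1, note n, says "Investigators may perform additional scans or more frequent assessments if clinically indicated". That note permits extra scans and says nothing about partial or single-region ones. This objection stands and limits frequency.

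**A partial scan might not be a tumor assessment at all.** Condition (a) would then hold. But Appendix 3 itself calls a partly measured scan an assessment, so the point is at best ambiguous, which is a reason to define the term.

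**NE is not automatic.** A reader might infer that any missing lesion makes the visit NE. Appendix 3 says only that this is usual, and names PD as the likeliest exception. This stands.

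**The patients exposed are few and selected.** A reader might picture deteriorating patients being scanned incompletely. Those who stop at PD with no later scan count under (a). Those rescanned are mainly treated beyond progression, and Protocol 4.6.2 requires them to have clinical benefit and no decline in performance status attributable to progression.

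**Requiring confirmation is deliberate, and efficacy is descriptive.** Both are true: the allowance for pseudo-progression is explained in Protocol 3.3.6, and SAP 3.4 makes all efficacy analyses descriptive and secondary. But an NE scan neither confirms nor refutes, so the purpose of confirmation does not justify dropping the PD.

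**Conclusion.** The gap is real on the text. It is confined to a PD followed by a scan that was done but is NE, and the direction is certain: modified RECIST PFS can only become longer. The same holds for DOR if it uses the same progression definition. SAP 3.4.1.6 implies this by its general wording and by summarizing PFS and DOR together, but the two conditions stand in the PFS paragraph and the DOR paragraph does not cite them.

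The size is unknown. The range of 3 to 65 patients per 600 rests wholly on the assumed scanning and NE rates, and within it the median usually does not change. A reader might infer a large inflation by supposing that 5% to 15% of all PDs end in an NE scan with nothing after it. The documents do not support such a share. The assumptions used here give 0.30 × 0.02 × 0.5 = 0.3% to 0.60 × 0.20 × 0.5 = 6%.

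RECIST v1.1 PFS and DOR, OS and both primary safety endpoints are unaffected. This is a modest flaw in secondary descriptive endpoints, worth correcting because the correction is nearly free.

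**What to change.** In SAP 3.4.1.6, state that:

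- the subsequent tumor assessment is the next evaluable one, meaning a modified RECIST overall response other than NE;
- if there is none, condition (a) applies;
- progression is dated at the first PD;
- the same definition is used for modified RECIST DOR.

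Do not add a 4-week minimum to condition (b) alone. A PD followed only by an evaluable scan at 2 or 3 weeks would then meet neither condition. If the Appendix 3 interval of at least 4 weeks is to apply, put it in both conditions.

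The cost is SAP wording and a filter on NE visits, with no new data, patients or procedures. Modified RECIST PFS and DOR will be slightly shorter. A pseudo-progression followed only by an NE scan will count as PD, as condition (a) already does when no scan follows.
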